5.1.1.1.2 Study Treatments

The following treatment groups and cohorts are defined for stage 1 in this study:

Cohort	Treatment Group
Cohort 5A	RESTASIS X F1
Cohort 4	RESTASIS X F1
Cohort 6C	RESTASIS X F1 with retreatment at week 12
Cohort 3	RESTASIS X F1
Cohort 2	RESTASIS X F1
Cohort 6B	RESTASIS X F2
Cohort 6D	RESTASIS X F2 with retreatment at week 12
Cohort 6A	RESTASIS X F2
Cohort 1	Vehicle

Data will be analyzed by treatment group/cohort, unless otherwise specified.

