5.1.1.1.3 Statistical Methodology

The methodologies defined in Table 5-2 apply as specified to individual endpoints defined in this SAP for stage 1.

Table 5-2 Statistical Methodology – Stage 1

Methodology	Description
Categorical counts	
 • Number of patients in individual categories 
 ○ Patients with ≥ 1 qualifying event counted once per individual category
Categorical descriptives	
 • Number and percentage of patients in individual categories 
 ○ Patients with ≥ 1 qualifying event counted once per individual category • N1 if percentage denominator \neq number of patients in the population (standard percentage denominator) 
 ○ N1 = patients with nonmissing value
Continuous descriptives	
 • N1, mean, SD, median, minimum, maximum • N1 = patients with nonmissing value
CFB descriptives	
 • Continuous descriptives for baseline, postbaseline, and CFB values • N1 = patients with nonmissing values at both baseline and the specified postbaseline analysis visit
Responder	
 • Categorical descriptives for responders and nonresponders • N1 = patients with nonmissing values at both baseline and the specified postbaseline analysis visit

CFB = change from baseline

Two treatment cycles are defined in this analysis plan. Treatment Cycle 1 includes all visits from study baseline (also called cycle 1 baseline) to Week 24 or Exit visit if a patient receives ██████████ throughout the study, or to the last visit before retreatment if a patient receives ██████████ during the study. For visits in treatment Cycle 1, refer to study windows in Section 6.2. Treatment Cycle 2 applies to patients who receive retreatment, and includes all visits from retreatment and thereafter. Visits in treatment Cycle 2 will be determined based on the study days relative to the retreatment visit using the study windows specified in Section 6.2.

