The study baseline value of an assessment will be the measurement prior to the treatment at Day 1 unless it is missing. In that case, the last nonmissing value recorded prior to the treatment (Day 1) will be used instead. The cycle baseline (also called cycle 2 baseline) value of an assessment will be the measurement prior to the retreatment at Week 12 from the first treatment unless it is missing. In that case, the last nonmissing value recorded prior to the retreatment (Week 12) will be used instead.

Ocular evaluation will be summarized by study eye and contralateral eye separately.

Some raw and derived data listings will be provided, and will be fully defined in the table, figure, and data listing specification document.

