5.1.1.4.1 Study Treatment Exposure

Study treatment exposure and compliance will be summarized by treatment group for the safety population as shown in [Table 5-16](#).

Table 5-16 Study Treatment Summaries

Parameter	Description	Timing	Methodology
Study treatment exposure (days)	Date of study exit – date of 1st injection + 1	Treatment period	Continuous descriptives

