5.1.1.4.2 Adverse Events

Adverse events (AEs) are defined as shown in [Table 5-17](#).

Table 5-17 AE Terms

Term	Description
TEAE	An adverse event recorded on the eCRF would be considered treatment-emergent if either of the following conditions are met: AE onset date \geq first study treatment date; or AE onset date $<$ first study treatment date and either: 
 • the severity of the event worsened on or after the first study treatment date, or • the event became serious on or after the first study treatment date
SeriousTEAE	An event identified as TEAE that further meets SAE criteria at any time would be a serious TEAE.

SAE = serious adverse event; TEAE = treatment-emergent adverse event

AEs, encompassing abnormalities and surgeries reported as occurring after the Screening Visit, will be coded using MedDRA version 19.0 or newer. Unique patients reporting AEs in the following AE categories will be summarized by treatment group for the safety population as shown in [Table 5-18](#).

Table 5-18 AE Summaries

Parameter	Description	Timing	Methodology
Overall summary	Overall summary for the following categories: 
 • TEAEs (ocular vs. non-ocular) • Study drug-related TEAEs (ocular vs. non-ocular) • Study procedure-related TEAEs (ocular vs. non-ocular) • Serious TEAEs (ocular vs. non-ocular) • TEAEs leading to study 	From treatment start date until Week 24/Week 12R or early termination date, whichever comes first	Categorical descriptives

Parameter	Description	Timing	Methodology
	
discontinuation (ocular vs. non-ocular)
 
 Deaths 		
TEAEs ^a	
Overall summary and by SOC in alphabetical order, PT and worst severity
 
The worst severity is defined as the greater of the onset severity and maximum severity following onset recorded on the eCRF. If the same TEAE term has been reported more than once for a subject with different severity grades, the worst severity grade will be used in the tabulation.
	
From treatment start date until Week 24/Week 12R or early termination date, whichever comes first
	Categorical descriptives

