5.1.1.4.3 Clinical Laboratory Assessments

Clinical laboratory assessments will be summarized by treatment group for the safety population as shown in [Table 5-19](#).

Table 5-19 Clinical Laboratory Summaries

Endpoint	Description	Timing	Methodology
Descriptives	Summary by laboratory category, parameter and analysis visit 
 Parameters specified in Table 6-22 	Cycle 1: Study baseline (screening), Week 12 (for Cohorts 6C and 6D only), and Week 24 Cycle 2: Cycle baseline and Week 12R	CFB descriptives

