5.1.1.7 Interim Analyses

An interim database lock of stage 1 will not be conducted until after all patients in Cohorts 1 through 6B complete the study and all patients in Cohorts 6C and 6D complete at least Week 1 following retreatment. Statistical analyses will be performed following the database lock to support the design of future clinical studies.

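### The adverse-event and slit-lamp summaries pool both treatment cycles, so for Cohorts 6C and 6D they do not show what happened after retreatment

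*SAP*

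**What the plan says.** All references are to the Stage 1 SAP unless stated.

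- **Window.** Every row of Table 5-18 (section 5.1.1.4.2) is timed "From treatment start date until Week 24/Week 12R or early termination date, whichever comes first". Table 5-23 (slit-lamp, section 5.1.1.4.5.3) carries the same timing. A TEAE is defined relative to the first study treatment date only.
- **Counting.** Table 5-2 sets the rule: "Patients with ≥ 1 qualifying event counted once per individual category". The TEAE and ocular TEAE rows are also tabulated by worst severity.
- **Cohorts.** Section 5.1.1.1.2 gives the retreated cohorts their own groups. Cohort 6C, for example, is "RESTASIS X F1 with retreatment at week 12". Section 5.1.2 plans 4 patients each for 6C and 6D.
- **Cycles.** Section 5.1.1.1.3 states: "Treatment Cycle 2 applies to patients who receive retreatment, and includes all visits from retreatment and thereafter". It adds a second reference point: "The cycle baseline (also called cycle 2 baseline) value of an assessment will be the measurement prior to the retreatment at Week 12".
- **Use of cycles elsewhere.** Laboratory tests are timed "Cycle 2: Cycle baseline and Week 12R" in addition to Cycle 1. Vital signs, visual acuity, macroscopic and photographic hyperemia and intraocular pressure are also shown by cycle. Table 5-24 (dilated examination) names Week 12 separately for 6C and 6D.
- **Slit-lamp event.** Table 5-23 counts a rise of at least one grade from baseline. It does not say whether this is study baseline or cycle 2 baseline.
- **Exposure.** Table 5-16 defines exposure as "Date of study exit – date of 1st injection + 1" and has no row for the number retreated.
- **Interim lock.** Section 5.1.1.7 allows the lock once Cohorts 1 to 6B have finished and "all patients in Cohorts 6C and 6D complete at least Week 1 following retreatment". The analyses that follow are meant to inform the design of future studies.
- **Retreatment can be withheld.** Protocol 5.10 lets the investigator withhold it in Stage 1, with the patient remaining under observation.

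**The concern.** Cohorts 6C and 6D are where Stage 1 can show how patients fare after a second administration. A reader would look first at the TEAE and slit-lamp tables. Those tables keep the retreated cohorts apart from the others, but within each cohort they merge the time before retreatment with the time after it. A patient whose only event came in the first twelve weeks looks the same as one whose only event followed retreatment.

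The SAP already has the definitions needed to separate the two periods and gives no reason for not using them here. The point matters most at the interim lock, when some patients may have only one week of follow-up after retreatment and the output is to be used for planning. The Amendment 6 summary mentions a Stage 1 safety hypothesis on retreatment. The hypothesis section itself is blacked out, so that is context only.

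**Working it through.** **Step 1. Denominators.** The planned sizes reproduce the stated maximum: 3 (Cohort 1) + 3 × 4 (Cohorts 2, 6C, 6D) + 6 × 8 (Cohorts 3, 4, 5A, 5B, 6A, 6B) = 63 patients in 10 cohorts. The tables in question therefore have n = 4 per retreated cohort, at most 8 patients in all. Let r be the number actually retreated in a cohort (r ≤ 4).

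**Step 2. What a pooled TEAE count implies.** For one category, each patient has no event, an event in Cycle 1 only, in Cycle 2 only, or in both. Let a be the number with Cycle 1 only. If the pooled count is k, the number with an event after retreatment is k − a, where a can be anything from 0 to k and the result cannot exceed r. Enumerating all patterns for n = 4 gives the compatible counts after retreatment:

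| Pooled k | r = 4 | r = 3 | r = 2 |
|---|---|---|---|
| 0 | 0 | 0 | 0 |
| 1 | 0–1 | 0–1 | 0–1 |
| 2 | 0–2 | 0–2 | 0–2 |
| 3 | 0–3 | 0–3 | 0–2 |
| 4 | 0–4 | 0–3 | 0–2 |

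With all four retreated, a pooled 3/4 fits 0/4 to 3/4 (0–75%). With three retreated, it fits 0/3 to 3/3 (0–100%).

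**Step 3. How often this would matter (illustration on an assumption).** The documents give no event rates. Assume the same independent risk p in each cycle and r = 4. The chance that a non-zero pooled count contains no patient with an event after retreatment is [(1−p)^4 − (1−p)^8] / [1 − (1−p)^8]. This is 0.40 for p = 0.10, 0.24 for p = 0.25 and 0.06 for p = 0.50.

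**Step 4. Severity cells.** Take a patient with a severe event in Cycle 1 and a mild event of the same term after retreatment. Only the worst grade is tabulated, so the patient appears as severe. The mild cell can read 0 although a mild event followed retreatment. Step 2 therefore applies to overall, organ-class and preferred-term counts, not to single severity cells.

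**Step 5. Slit-lamp.** Take an eye graded 2 at study baseline, 1 at Week 12 before retreatment, and 2 afterwards.

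- From study baseline, the changes are 1 − 2 = −1 and 2 − 2 = 0, so no increase is counted.
- From cycle 2 baseline, the change is 2 − 1 = +1, so an increase is counted.

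If Table 5-23 means study baseline, its pooled count is not an upper bound on rises from the cycle 2 baseline, and a pooled zero does not exclude them.

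**Step 6. Follow-up at the interim lock.** Using the SAP target days (retreatment at day 84, Week 1R at 7 days), a patient at the minimum has 7 of 84 + 7 = 91 days after retreatment, or 7.7%. At Week 12R the share is 84/168 = 50%. These are shares of follow-up time, not of events.

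**The case against.** The strongest reply is that little is lost. At most 8 patients are involved. The protocol (section 7.3.1) asks for numbers and percentages of patients with TEAEs, split into ocular and nonocular, and the SAP delivers that. A footnote to Table 5-18 promises a listing of all adverse events, and section 6.2 promises listings of all assessments, so the split can be rebuilt by hand if dates are shown. Several other safety measures are already reported by cycle. The table specifications are in a separate document that was not available and may already include a by-cycle display. The number retreated might also emerge from the disposition table by phase (Table 5-4), since Tables 6-10 to 6-15 label retreatment as an analysis phase. Its stated timing is only the treatment period, so that is not conclusive.

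All of this limits the weight of the point but does not remove it: the summary tables, as specified, do not isolate the period after retreatment.

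Three stronger readings are tempting and not supported:

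- **The pooled count is always a safe ceiling.** Steps 4 and 5 show that it is not, within severity cells or for slit-lamp rises from the cycle 2 baseline.
- **Interim counts mostly reflect the first treatment, because 7 of 91 days is a small share.** That needs a constant event rate. If events cluster soon after each administration, the time share says little about which cycle produced them. Week 1R is also only a minimum.
- **The partial-date rule is a defect.** Imputing onset toward first treatment does no harm while the tables are pooled. It matters only once a split is added.

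**Conclusion.** The point holds in a limited form. For Cohorts 6C and 6D, a non-zero TEAE count in Table 5-18 at overall, organ-class or preferred-term level is compatible with anything from no patients to k patients (or r, if smaller) having an event after retreatment. A zero at those levels does mean zero. For slit-lamp, the unspecified baseline is the sharper problem: under the study-baseline reading, even a pooled zero does not rule out worsening from the grade just before retreatment.

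A reader might infer that retreatment safety goes unreported, or that cohorts are mixed. Neither is so. Cohorts are separate groups, and Cycle 2 rows and listings cover part of the question.

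The conclusion rests on the SAP text and cohort sizes alone. The chances in Step 3 are illustrative, and the unseen table specifications could already close the gap. This is a change that could usefully be made, not a failure of the safety plan.

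**What to change.** Keep the pooled tables. For Cohorts 6C and 6D, add:

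1. **TEAE summaries by cycle** (all, ocular, drug-related, procedure-related, serious), assigned by onset before the retreatment date versus on or after it. Footnote events ongoing at retreatment.
2. **Slit-lamp grade increases at Cycle 2 visits**, measured from the cycle 2 baseline. State which baseline the pooled Table 5-23 uses.
3. **The numbers retreated and not retreated**, with the number retreated as the Cycle 2 denominator.

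As an implementation note only, flag partial onset dates that could fall on either side of retreatment. Tables 6-16 and 6-17, with first treatment as target (section 6.3.1), would place most of them in Cycle 1. Assuming retreatment 84 days after first treatment and trying each of the 365 start dates in an assumed year (2017), an onset known only to the month of retreatment is placed before retreatment for 353 of 365. A fully missing date is placed there for 365 of 365. The number of partial dates is unknown.

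The cost is SAP wording and a few more descriptive tables from data already collected, with no new assessments. The downside is denominators of at most 4. The exact (Clopper-Pearson) 95% interval is 0–60% for 0/4 and 19–99% for 3/4, so the added rows describe individual patients and should not be read as rates.

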7.3.1 Safety Analyses

Safety measures will be analyzed using the safety population. The Medical Dictionary for Regulatory Activities (MedDRA) nomenclature will be used to code adverse events. The number and percentage of patients with treatment-emergent adverse events will be summarized. The adverse events will be classified into ocular and nonocular types and will be summarized separately. Detailed methods for the analyses of adverse events and other safety variables will be described in the SAP.

[REDACTED]

[REDACTED]

Approval Date: 19-Jan-2017

[Redacted]

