8.14 Procedures for Reporting a Serious Adverse Event

Any serious adverse event occurring during the study period (beginning with informed consent) and for at least 12 weeks after the last dose of study drug must be immediately reported, but no later than 24 hours after learning of a serious adverse event. Serious adverse events must be reported to Allergan (or Agent of Allergan) as listed on the Allergan Study Contacts Sheet and recorded on the serious adverse event form. All patients with a serious adverse event must be followed up and the outcomes reported. The investigator must supply Allergan and the IRB/IEC with any additional requested information (eg, autopsy reports and discharge summaries).

In the event of a serious adverse event, the investigator must:

1. Notify Allergan immediately by fax or email using the serious adverse event form (contact details can be found on page 1 of the serious adverse event form); phone numbers and relevant Allergan personnel contacts are also on the front page of the protocol.
2. Obtain and maintain in his/her files all pertinent medical records, information, and medical judgments from colleagues who assisted in the treatment and follow-up of the patient.
3. Provide Allergan with a complete, written description of the adverse event(s) on the serious adverse event form describing the event chronologically, including any treatment given (eg, medications administered, procedures performed) for the adverse event(s). Summarize relevant clinical information about the event: signs, symptoms, diagnosis, clinical course and relevant clinical laboratory tests, etc. Include any additional or alternative explanation(s) for the causality which includes a statement as to whether the event was or was not related to the use of the investigational drug.
4. Promptly inform the governing IRB/IEC of the serious adverse event as required by the IRB/IEC, local regulations, and the governing health authorities.

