Ocular TEAEs	
Overall summary and by SOC in alphabetical order, PT and worst severity
 
The worst severity is defined as the greater of the onset severity and maximum severity following onset recorded on the eCRF. If the same TEAE term has been reported more than once for a subject with different severity grades, the worst severity grade will be used in the tabulation.
	
From treatment start date until Week 24/Week 12R or early termination date, whichever comes first
	Categorical descriptives
Study drug-related ocular TEAEs	
Overall summary and by SOC in alphabetical order and PT
	
From treatment start date until Week 24/Week 12R or early termination date, whichever comes first
	Categorical descriptives
Study procedure-related ocular TEAEs	
Overall summary and by SOC in alphabetical order and PT
	
From treatment start date until Week 24/Week 12R or early termination date, whichever comes first
	Categorical descriptives
Serious TEAEs	
Overall summary and by SOC in alphabetical order and PT
	
From treatment start date until Week 24/Week 12R or early termination date, whichever comes first
	Categorical descriptives
TEAEs leading to study discontinuation	
Overall summary and by SOC in alphabetical order and PT
	
From treatment start date until Week 24/Week 12R or early termination date, whichever comes first
	Categorical descriptives

eCRF = electronic case report form; PT = preferred term; SAE = serious adverse event; SOC = system organ class;
TEAE = treatment-emergent adverse event

^a All AEs including pretreatment AEs and TEAEs, and SAEs will be listed.

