6.3.3 Missing/Incomplete AE/Medication End Date

AE and medication end dates will be imputed as the minimum of the following:

- Initial imputed date, where target date = from treatment start date until Week 24/Week 12R or early termination date, whichever comes first
- Death date

		
---	--	---

[REDACTED]

[REDACTED]

[REDACTED]

[REDACTED]	[REDACTED]	[REDACTED]
[REDACTED]	[REDACTED]	[REDACTED]
[REDACTED]	[REDACTED]	[REDACTED]
[REDACTED]	[REDACTED]	[REDACTED]

[REDACTED]

[REDACTED]

[REDACTED]	[REDACTED]	[REDACTED]
[REDACTED]	[REDACTED]	[REDACTED]
[REDACTED]	[REDACTED]	[REDACTED]

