6.5 Safety Endpoint Conventions

6.5.1 Adverse Events

6.5.1.1 Missing Intensity or Relationship

If the investigator is unable to provide the actual values, the imputations will be applied as shown in [Table 6-21](#).

Table 6-21 Missing AE Intensity and Relationship Imputation Algorithms

Missing Value	Imputation	Timing
Intensity	Mild	Screening Period
	Severe	Treatment Period
Relationship	—	Screening Period
	Related	Treatment Period

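### No row of SAP Table 5-18 counts a serious adverse event or death after early termination, although Protocol 8.14 keeps SAE reporting open for at least 12 weeks after the last dose

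*SAP*

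**What the plan says.** SAP 5.1.1.4.2, Table 5-18, has seven rows: the overall summary (which holds the serious TEAE and Deaths lines), all TEAEs, ocular TEAEs, drug-related ocular TEAEs, procedure-related ocular TEAEs, serious TEAEs, and TEAEs leading to study discontinuation. All seven have the same entry under Timing: "From treatment start date until Week 24/Week 12R or early termination date, whichever comes first".

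Table 5-17 in the same section defines the events to be counted: "An adverse event recorded on the eCRF would be considered treatment-emergent if either of the following conditions are met". Both conditions concern the start of the event or its worsening relative to first treatment. Neither sets a last date, and a serious TEAE is one that meets the seriousness criteria at any time.

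Protocol 8.14 sets the SAE reporting period. It begins at consent and continues during the study "and for at least 12 weeks after the last dose of study drug must be immediately reported". No exception is stated for patients who withdraw. Protocol 8.12.2 includes death among the outcomes that make an event serious.

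Footnote a to Table 5-18 says "All AEs including pretreatment AEs and TEAEs, and SAEs will be listed", with no time limit. Protocol 7.3.1 delegates the detail: "Detailed methods for the analyses of adverse events and other safety variables will be described in the SAP".

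**The concern.** The SAP's definition of a serious TEAE admits an event that starts after a patient has left, and the protocol requires that event to be reported. The Timing column alone then removes it from every count.

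Early exit may also be related to health. Protocol 8.9 says patients should be discontinued when a new or worsening medical condition puts them at unacceptable risk. Protocol 4.5.1.1 has pregnant patients exit after safety follow-up, and Protocol 8.12.2 treats any abortion as serious. The protocol therefore contains routes to a reportable event after exit.

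Safety is the first-named stage 1 objective, cohorts have 3 to 8 patients, and SAP 5.1.1.7 says the analyses are meant to support the design of later studies. A zero in the Deaths or Serious TEAEs line would be read as no such event in that cohort.

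**Working it through.** **1. Which events fall between the definitions**

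| Source | Start | End |
|---|---|---|
| Table 5-17, TEAE and serious TEAE | first study treatment | none stated |
| Protocol 8.14, SAE reporting | informed consent | at least 12 weeks after last dose |
| Table 5-18, all seven rows | treatment start | earlier of Week 24/Week 12R and early termination |

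An SAE that starts after early termination but within 12 weeks of the last dose meets the first two and fails the third.

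**2. Length of the untabulated period**

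Let t be the days from last dose to the early termination date. The minimum reporting period is 12 × 7 = 84 days.

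Untabulated days = max(0, 84 - t)

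- t = 14: 84 - 14 = 70 days
- t = 28: 84 - 28 = 56 days
- t = 56: 84 - 56 = 28 days
- t ≥ 84: 0 days

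Counting the dosing day as Day 1, as SAP Table 6-1 does, adds one day for a single-dose patient who exits on the target day: Week 2 is Day 14, so t = 13 and the period is 71 days. A patient who completes at the nominal Week 24 or Week 12R has essentially no untabulated period.

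**3. Deaths**

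The Deaths line carries the same Timing, read here as applying to the date of death. Suppose a single-dose patient leaves 100 days after dosing and dies 10 days later from an SAE that began before exit. Step 2 gives 0 untabulated days for new SAEs, and the SAE itself is counted because it began on study. The death still falls outside the window. The omission of deaths is therefore not limited to exits before 84 days.

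**4. How many patients could be affected**

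The plan's stage 1 total is reproduced from its cohort sizes (SAP 5.1.2): 3 + 3 × 4 + 6 × 8 = 63. The cohort list in SAP 5.1.1.1.2 has no Cohort 5B, which gives 3 + 3 × 4 + 5 × 8 = 55. Each patient has one last dose and leaves once, so at most one such period applies per patient. The ceiling is 63 (or 55), and only early leavers count towards it.

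**5. Effect on a table cell**

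If one such event occurred and were the cohort's only one:

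- n = 8 (Cohorts 3, 4, 5A, 6A, 6B, and 5B if enrolled): 0% shown instead of 1/8 = 12.5%
- n = 4 (Cohorts 2, 6C, 6D): 0% instead of 1/4 = 25%
- n = 3 (Cohort 1, vehicle and sham only): 0% instead of 1/3 = 33.3%

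These are sizes for a single hypothetical event, not estimates. The documents give no dropout or SAE rate.

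**The case against.** The strongest reply is that an on-study window for descriptive tables is a legitimate choice, that Protocol 7.3.1 leaves such choices to the SAP, and that all SAEs are listed. In cohorts this small a reader can find one SAE in a listing. Unretreated patients stay under observation to the Week 24 exit (Protocol 5.10), and leavers are encouraged to return for exit procedures (Protocol 8.8), so the affected group may be very small.

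Most of this stands, and it limits the weight of the point. It does not remove it: a listing shows the event but leaves the zero in the summary count uncorrected.

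A reader might also infer more than the documents support:

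- *The SAP contradicts the protocol.* It does not. Protocol 8.14 governs reporting and Table 5-18 governs tabulation.
- *The event may never reach the database*, because Table 5-17 relies on the eCRF while 8.14 has SAEs reported "and recorded on the serious adverse event form". Protocol 8.13 requires every adverse event to be entered on the eCRF, with no time limit stated, and 8.14 does not say that the SAE form replaces that entry.
- *Every dosing opens its own period*, giving 63 + 8 = 71. Protocol 8.14 runs from the last dose, so retreated patients do not count twice.
- *The imputation rules also need changing.* SAP 6.3.3 sets the end-date target as "Initial imputed date, where target date = from treatment start date until Week 24/Week 12R or early termination date, whichever comes first", which could place an imputed end before the onset of a post-exit event. No Table 5-18 row uses an end date, start-date imputation (6.3.1) uses only a complete end date, and listings show the actual values (6.7). Similarly, 6.5.1.1 says "If the investigator is unable to provide the actual values, the imputations will be applied as shown in" Table 6-21, but a count of patients with an SAE or death does not depend on intensity or relationship.
- *Dose escalation is affected.* Nothing in the readable text links these tables to escalation decisions.

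**Conclusion.** The point holds as a narrow gap in summary reporting. For a patient who leaves t < 84 days after the last dose, SAEs starting in the remaining 84 - t days of the minimum reporting period are listed but counted nowhere. A death after early exit is missing from the Deaths count whatever the time since the last dose. Completers are unaffected.

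The number of such events is unknown and may be zero. The possible consequence is a cohort shown at 0% instead of 12.5%, 25% or 33.3%.

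This rests on three assumptions. First, t is measured to the early termination date, which the readable text does not define; if a later exit visit sets that date, the period is shorter. Second, the Timing column applies to the onset of an SAE and to the date of a death. Third, the separate table specification mentioned in SAP 4, which was not available, contains no row for these events.

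**What to change.** Leave the seven on-study rows, their Timing and the TEAE definition as they are. Add one row to Table 5-18 that counts patients with an SAE or death reported after early termination. Its window should cover at least the 12 weeks after the last dose that Protocol 8.14 requires, and any later death that is reported. It should not stop at 12 weeks, because 8.14 sets a minimum and a stop there would miss the death in step 3 of the working. A footnote should say that these events are passively captured. If the separate table specification already has such a row, a pointer to it in the SAP is enough.

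The cost is one row and one footnote. No new data collection is needed for the SAEs that 8.14 already requires. The drawback is that passively captured events appear beside actively collected ones, which is why they should have their own row and not be merged into the existing counts.
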